- Motility disorders that affect the upper gastrointestinal tract (i.e. chronic pseudo-obstruction, severe gastroparesis) or motility disorders that are poorly controlled
- Unable to discontinue medications that directly alter fat absorption (i.e. bile acid sequestering agents, orlistat, weight loss medications, ursodeoxycholic acid) for one week prior to the first blood draw for the study until completion of stool collection following study visit 2 based on the preference of the subject or primary gastroenterologist. Permission must be obtained from the primary gastroenterologist before discontinuing medications in this category.
- Cholestatic liver disease defined as a serum conjugated bilirubin greater than 1.0 mg/dL), chronic renal failure requiring dialysis or listed for kidney transplant, or gout
- History of a pork allergy
- Candidate for intestinal transplantation and listed as status 1
- Women who are pregnant or lactating

	
 • History of fibrosing colonopathy 
MBT/CCK Subset Exclusion Criteria
 
 • History of a soy or safflower oil allergy
Number Of Subjects	
Non-MBT/CCK Subset: 16 subjects with SBS between the ages of 4 years and 17.9 years
 
MBT/CCK Subset: 10 subjects with SBS between the ages of 18 years and 75 years, subjects will have the option not to perform the MBT

Study Location	All study visits will occur at outpatient research offices at the Clinical and Translational Research Center of the Children's Hospital of Philadelphia (CHOP), a pediatric health care center.
Study Duration	Subject participation will last about 3-4 weeks.

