Exploratory aspects of the study also address the changes that nutrient absorption will have on intestinal adaptation and enteroendocrine hormone signaling. Intestinal adaptation refers to the process of improving and maximizing the absorptive capacity of the residual intestine in patients with SBS. It is clear that intestinal resection alters enteroendocrine hormone signaling^{6,18}. Alterations in enteroendocrine hormone signaling impact both intestinal absorption and transit. As mentioned, repletion of one intestinal hormone, GLP-2, does improve absorptive capacity of the small intestine³.

Endocrine hormones, such as CCK, stimulate proper digestion of triglyceride for fat absorption, but then free fatty acids also mediate downstream endocrine signaling. It is clear that the type of macronutrient, as well as the phase of digestion are both important contributors in the stimulation of enteroendocrine cells¹⁹. For example, an undigested lipid does little to stimulate enteroendocrine hormone secretion, whereas free fatty acids and monoacylglycerols bind to specific receptors to stimulate hormone secretion, such as GLP-2. Patients with SBS have impaired secretion of GLP-2, which is associated with poor intestinal growth and absorption⁶. Removal of bowel also results in resection of enteroendocrine cells, which explains part of the change in hormonal signaling. One study²⁰ demonstrated that rats with a significant bowel resection demonstrated improved small bowel growth and adaptation with exposure to GLP-2 and enteral nutrition together compared to enteral nutrition alone, GLP-2 alone, or parenteral nutrition. Thus, not only do enteric hormones allow for proper digestion and absorption, but proper digestion also stimulates intestinal growth. This study also highlights that the delivery of nutrients into the bowel plays a crucial role in hormone signaling.

Several markers of intestinal adaption exist. Insulin-like growth factor 1 (IGF-1) is thought to play a key role in intestinal growth, specifically in that it likely serves downstream of the action of GLP-2^{20,21}. Though it is produced primarily by the liver, IGF-1 is also thought to be produced locally in the intestine. Data on growth hormone and IGF-1 in humans has been conflicting, though a study by

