4.4 Open-Label Treatment with Creon™

Subjects will receive open-label treatment with Creon™ as their pancreatic enzyme medication therapy and will receive this therapy for nine days encompassing Study Visit #2. There are two protocols for Study Visit #2. The first protocol is for subjects in the non-MBT/CCK cohort and the second protocol is for subjects in the MBT/CCK cohort. Please note that subjects who are eligible for the MBT/CCK subset and decline the MBT will follow the same protocol as the non-MBT/CCK subset.

Study Visit #2: Pancreatic Enzyme Medication Treatment Protocol for Subjects in the non-MBT/CCK Subset

Days 1 -4

- Pancreatic enzyme medication treatment
- Subject's normal diet

Day 5 – CHOP Visit to CTRC Outpatient Lab and NGL

- Subject's normal diet
- Pancreatic enzyme medication treatment

- Blood draw: pre-albumin, citrulline, IGF-1, IGF BP3, GLP-2, GH, CBC, CMP, hepatic function panel
- Spot stool sample will be collected for stool pH
- If subject has a G tube, spot gastric pH will be checked
- Adherence to pancreatic enzyme medication and Adverse Events Questionnaires
- Instructions will be given for collection and shipping for: stool collection (72-hour fecal fat, 72-hour fecal nitrogen, and bomb calorimetry), 3-day weighed food records, and adverse events diary

Day 6 - Home

- Pancreatic enzyme medication treatment
- Subject's normal diet
- Maintain adverse events diary

Day 7 - Home

- Pancreatic enzyme medication treatment
- Subject's normal diet
- 3-day weighed food records begins
- Food record – Day 1
- Maintain adverse events diary

Day 8 - Home

- Pancreatic enzyme medication treatment
- Subject's normal diet
- Food record – Day 2
- Stool collection (72-hour fecal fat, 72-hour fecal nitrogen, and bomb calorimetry), store frozen until brought to CHOP.
- 72-hour stool – Day 1
- Maintain adverse events diary

Day 9 - Home

- Pancreatic enzyme medication treatment
- Subject's normal diet
- Food record – Day 3
- 72-hour stool – Day 2
- Maintain adverse events diary

Day 10 - Home

- Pancreatic enzyme medication treatment

- Subject's normal diet
- 72-hour stool – Day 3
- Maintain adverse events diary

Day 11 - Home

- Subjects who had discontinued a medication that directly alters fat absorption for this study can resume this medication as it was prescribed by their primary physician

Study Visit #2: Pancreatic Enzyme Medication Treatment Protocol for Subjects in the MBT/CCK Subset

Days 1, 2, & 3

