- Pancreatic enzyme medication treatment
- Subject's normal diet

Day 4

- Pancreatic enzyme medication treatment
- Subject's normal diet except for no dairy intake
- No alcohol intake
- Normal daily activity
- Fast overnight starting at 8pm

Day 5 – CHOP Visit to CTRC Outpatient Lab and NGL

- Pancreatic enzyme medication treatment
- Insert heplock catheter
- Blood draw: baseline blood draw for MBT, pre-albumin, citrulline, IGF-1, IGF BP3, GH, CBC, CMP, hepatic function panel, baseline CCK, baseline GLP-2
- Administer MBT study meal (breakfast)
- MBT – hourly blood sample for 8 hours
- Blood sample for CCK concentration at 1 hour
- Blood sample for GLP-2 concentration at 1 hour and 2 hours
- After hour 6 a low fat study lunch
- Adherence to pancreatic enzyme medication and Adverse Events Questionnaires
- Instructions will be given for collection and shipping for: stool collection (72-hour fecal fat, 72-hour fecal nitrogen, and bomb calorimetry), 3-day weighed food records, and adverse events diary
- Spot stool sample will be collected for stool pH
- If subject has a G tube, spot gastric pH will be checked

Day 6 - Home

- Pancreatic enzyme medication treatment
- Subject's normal diet
- Maintain adverse events diary

Day 7 - Home

- Pancreatic enzyme medication treatment
- Subject's normal diet
- 3-day weighed food records begins
- Food record – Day 1
- Maintain adverse events diary

Day 8 - Home

- Pancreatic enzyme medication treatment
- Subject's normal diet
- Food record – Day 2
- Stool collection (72-hour fecal fat, 72-hour fecal nitrogen, and bomb calorimetry), store frozen until brought to CHOP
- 72-hour stool – Day 1
- Maintain adverse events diary

Day 9 - Home

- Pancreatic enzyme medication treatment
- Subject's normal diet
- Food record – Day 3
- 72-hour stool – Day 2
- Maintain adverse events diary

Day 10 - Home

- Pancreatic enzyme medication treatment
- Subject's normal diet
- 72-hour stool – Day 3
- Maintain adverse events diary

Day 11 - Home

- Subjects who had discontinued a medication that directly alters fat absorption for this study can resume this medication as it was prescribed by their primary physician

Study Visit #3: Follow-Up Visit for All Subjects

Subjects will have the option to complete this visit via telephone. Questions on adverse events and medication adherence will be asked via telephone. Stool collection and diet records can be mailed or dropped off.

Days 1

- Adverse events monitoring

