Descriptive statistics (mean, standard deviation, median, range, 95% CI) will also be employed to assess outcomes related to intestinal hormone signaling that controls pancreatic enzyme secretion and intestinal adaptation in **H4** (glucagon-like peptide 2, insulin-like growth factor 1, insulin-like growth factor binding protein 3, and growth hormone concentrations). All variables will be tested for normality and nonparametric tests used as appropriate. The change in status for these variables before and after PERT administration will be explored with paired t-tests and Wilcoxon sign rank tests depending on skewness.

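### GLP-2 in the non-MBT schedule is drawn with no fixed feeding state, and the H4 analysis does not say which GLP-2 value it tests

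*Combined protocol and SAP*

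**What the plan says.** **Who follows which schedule.** The synopsis plans two groups: "Non-MBT/CCK Subset: 16 subjects with SBS between the ages of 4 years and 17.9 years" and "MBT/CCK Subset: 10 subjects with SBS between the ages of 18 years and 75 years, subjects will have the option not to perform the MBT". Section 4.4 adds that "subjects who are eligible for the MBT/CCK subset and decline the MBT will follow the same protocol as the non-MBT/CCK subset".

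**Non-MBT draws.** At Visit 2 the entry is "Blood draw: pre-albumin, citrulline, IGF-1, IGF BP3, GLP-2, GH, CBC, CMP, hepatic function panel", and the diet instruction for that day is "Subject's normal diet". The two non-MBT protocols for Visit 1 in Section 4.2 likewise have one draw containing GLP-2, on normal diet. Neither they nor Table 4 gives a fast, a clock time or an interval since feeding.

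**MBT draws.** These subjects fast from 8 pm, and Table 3 puts the MBT at 8 am. A baseline GLP-2 is taken before the test meal, followed by this entry: "Blood sample for GLP-2 concentration at 1 hour and 2 hours". The pattern is the same at both visits.

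**Mechanism.** Section 1.5 contrasts undigested lipid, which stimulates little hormone release, with digestion products: "free fatty acids and monoacylglycerols bind to specific receptors to stimulate hormone secretion, such as GLP-2".

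**Analysis.** For the H4 hormones Section 6.3.1 states: "The change in status for these variables before and after PERT administration will be explored", by paired t-test or Wilcoxon test. It names no subset, feeding state or GLP-2 time point. Section 6.2 presents this aim as exploratory.

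**The concern.** H4 asks whether enzymes raise GLP-2 by releasing free fatty acids. On the protocol's own account, fat recently digested also raises GLP-2. If a child is sampled soon after a feed at one visit and several hours after a feed at the other, GLP-2 can change with no enzyme effect at all. Section 1.4 expects oral meals, bolus feeds, overnight feeds and near-continuous feeds, so time since feeding may vary widely.

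The information probably cannot be recovered afterwards. The weighed food record starts two days after each visit (Day 10 after the Day 8 visit; Day 7 after the Day 5 visit). The 24-hour recall falls at Visit 1 only for subjects who sign consent there, and none is scheduled at Visit 2.

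Separately, each MBT subject has three GLP-2 values per visit. A fasting value and a post-meal value answer different questions, and the plan leaves the choice open.

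**Working it through.** **1. The two schedules side by side**

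| | Non-MBT | MBT |
|---|---|---|
| Subjects | 16 planned, up to 26 if every adult declines | up to 10 |
| GLP-2 samples per visit | 1 | 3 (0, 1 and 2 h) |
| State at the draw | normal diet, interval not set | fasted from 8 pm, then standard meal |
| Clock time | not set | MBT at 8 am |
| Value used for H4 | the only one | not stated |

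**2. What a paired change removes.** Each subject follows the same schedule at both visits. Write the change as D = enzyme effect + (feeding state at Visit 2 − feeding state at Visit 1) + other variation. A constant fed-versus-fasted difference between subsets drops out. What stays is the within-subject difference in feeding state, in the non-MBT schedule only.

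**3. Is there a planned figure to reproduce?** Not for H4: Section 6.4 gives no effect, SD or power for GLP-2. The nearest is CFA. With n = 22, difference 9, SD of differences 14 and two-sided 0.05, the noncentral-t power is 82% against the stated 80%, and the smallest n for 80% is 21. The paired-t framework therefore matches the plan's own.

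**4. Noise (illustration).** Assumptions: 16 + 10 subjects, a combined paired t-test, a true effect of 0.573 SD of change (80% power at n = 26), and feeding state adding k times the change variance in the 16.

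- Variance of the mean change is multiplied by 1 + (16/26)k.
- Noncentrality is 0.573 × √26 / √(1 + 16k/26) = 2.92 / √(1 + 16k/26).

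| k | Variance factor | Noncentrality | Power (40,000 simulated trials) |
|---|---|---|---|
| 0 | 1.00 | 2.92 | 80% |
| 0.5 | 1.31 | 2.55 | 69.0% |
| 1 | 1.62 | 2.30 | 60.2% |
| 2 | 2.23 | 1.96 | 47.6% |

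A repeat with 100,000 trials agrees within one point, and type I error stays near 5%. If all ten adults declined the MBT, the factor would be 1 + k and power 63%, 51% and 37%. With 14 + 8 evaluable subjects and the CFA-sized effect (9/14 = 0.643 SD), power goes from 82% to 71%, 62% and 48%.

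**5. Bias (only if the shift is systematic).** With no enzyme effect, a shift of 0.25 or 0.5 SD in all 16 gives a combined mean change of 16/26 × 0.25 = 0.15 or 16/26 × 0.5 = 0.31 SD. The false-positive rate becomes 11% or 30%.

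**6. Choice of GLP-2 value.** If enzymes acted only in the fed state and the ten fasting values were combined with the 16 fed ones, the mean effect would be 16/26 × 0.573 = 0.35 SD and power about 38%. This is why the measure needs naming.

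**The case against.** The other side has several good arguments, and most of them stand.

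- **Confounding with the enzyme effect.** A reader might infer that the fasted/fed split between subsets is itself mixed into the treatment effect. It is not: step 2 shows that a constant difference cancels. Unsystematic variation adds noise only, and nothing in the documents suggests that visit times shift systematically.
- **Pooling.** A reader might take it as settled that H4 is one test over the whole cohort. Section 6.3.1 refers to the SBS cohort for CFA, CNA and BC, but its H4 text neither states pooling nor provides a split. The supportable point is that the text is silent.
- **GH.** GH is drawn under the same differing conditions, so a reader might extend the point to it. The documents tie meal state to GLP-2 only, so a meal-state claim for GH is not supported.
- **Separate tests.** Splitting could cost more than it saves. At 0.573 SD, n = 16 gives 57% power and n = 10 gives 37%, even with perfect timing. Both are below the 69% and 60% that remain in a combined test at k = 0.5 and 1.
- **Continuous feeds.** Time since the last feed means little for subjects fed 20 to 24 hours a day, so a timing rule must be worded for them.
- **Importance.** The aim is exploratory.

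None of this removes the two remaining gaps: feeding state is neither set nor recorded at the non-MBT draws, and the GLP-2 measure is not named.

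**Conclusion.** The point holds as a cheap improvement to an exploratory aim. Followed as written, the plan allows feeding state to differ between a non-MBT subject's two GLP-2 draws. The protocol's own rationale says this matters for GLP-2. The result is a noisier change, with bias only under a systematic shift. The plan also leaves open which MBT-subset value is tested and whether the subsets are combined.

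The size cannot be derived from the documents. The fall from 80% to between about 69% and 48% rests on an assumed effect, an assumed 0.5- to 2-fold added variance, a 16/10 split and a combined test. A reader might take those figures as the expected loss; they show only how sensitive the test would be. CFA, CNA and BC do not depend on these draws.

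**What to change.** **Sections 4.2 and 4.4, non-MBT schedules.** Schedule each subject's Visit 1 and Visit 2 draws at the same clock time and in the same feeding state: the same interval since the last meal or bolus or, for continuous feeds, the same point in the feed. Record the clock time and feeding state at each draw. Matching each subject to their own first visit is enough; no common fast is needed.

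**Section 6.3.1, H4.** Name the GLP-2 measure for the MBT subset: the fasting value, and the 1 h and 2 h increments over it. State whether the subsets are combined. Show the GLP-2 change by subset descriptively beside any combined test, rather than replacing that test with two smaller ones. As only adults can be in the MBT subset, the by-subset display will partly reflect age and should be labelled so.

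**Cost.** Slightly less flexible appointment times and two extra fields on the case report form. No added samples or visits, and no change to the sample size.

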Participants discontinuing pancreatic enzyme medication will be without this medication for the nine days encompassing Visit 1.

Day 1-4 - Home

- Those subjects who are on a medication that directly alters fat absorption will discontinue this medication after permission is obtained from their primary gastroenterologist. Study team must have a signed, informed consent form prior to discontinuation of medication.
- Subject's normal diet

Days 5, 6, & 7

- Discontinue pancreatic enzyme medication (Washout) Subject's normal diet

Day 8 – CHOP Visit to CTRC Outpatient Lab and NGL

- Sign informed consent form if study visit 0 conducted via telephone for those subjects who do not have to discontinue medication or have labs at study visit 0
- 24-hour dietary recall for those subjects who sign the informed consent form at study visit 1
- Urine pregnancy test for pre-menopausal females
- Subject's normal diet
- Baseline blood draw: Fat soluble vitamins (A, D, E, K)*, pre-albumin, serum zinc*, selenium*, fatty acid profile*, citrulline, IGF-1, IGF BP3, GLP-2, GH, CBC, CMP, hepatic function panel
- Anthropometry (height, weight, skinfolds, circumferences)
- Whole body DXA
- Spot stool sample will be collected for stool pH and fecal elastase. Subjects who are unable to produce a sample at the visit will collect and freeze a stool sample at home on one occasion on Day 8, 9, or 10.
- If subject has a G tube, spot gastric pH will be checked
- Questionnaires: Health History and medications, Home Environment, Quality of Life (MOS SF-36 or PedsQL)
- Instructions will be given for collection and shipping for: stool collection (72-hour fecal fat and nitrogen analysis and bomb calorimetry), 3-day weighed food records, and adverse events diary
- Prescribe Creon™ and dispense to subjects

Day 9 - Home

- Subject's normal diet

- Maintain adverse events diary

Day 10 - Home

- Subject's normal diet
- 3-day weighed food record begins
- Food record – Day 1
- Maintain adverse events diary

Day 11 - Home

- Subject's normal diet
- Food record – Day 2
- Stool collection begins (72-hour fecal fat, 72-hour fecal nitrogen, and bomb calorimetry), store frozen until brought to CHOP.
- 72-hour stool – Day 1
- Maintain adverse events diary

Day 12 - Home

- Subject's normal diet
- Food record – Day 3
- 72-hour stool – Day 2
- Maintain adverse events diary

Day 13 - Home

- Subject's normal diet
- 72-hour stool – Day 3
- Maintain adverse events diary

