5.3 Safety Evaluation

Safety will be monitored by adverse events reporting. The frequencies of AEs by type, body system, severity and relationship to study supplement will be summarized. SAEs (if any) will be described in detail.

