* Will not exceed maximum daily enzyme dosing of 10,000 lipase units/kg/day

⁺ The dose of enzymes with each bolus depends on the enteral feeding regimen, grams of fat, and the volume and number of boluses

Bolus feeds: The dose of enzymes that each subject receives prior to each bolus will depend on the volume and total number of boluses received per day. We will attempt to cover each bolus with a maximum dose of 1500 – 2500 lipase units/kg/meal, but this may be reduced if boluses are smaller in volume or occur frequently.

Overnight feeds: This group includes subjects on overnight enteral feeds for 8-12 hours. These subjects will receive one meal dose of Creon™ (1500 - 2500 lipase units/kg) prior to feeds and one meal dose of Creon™ at the end of feeds, consistent with our current practice at CHOP.

Continuous feeds: This group includes those subjects on continuous enteral feeds for 20-24 hours of the day. For these subjects, we will dose enzymes every 4 hours while awake based on grams of fat in the formula and based on recommended dosing per grams of fat. Overnight, they will receive one meal dose of Creon™ (1500 – 2500 lipase units/kg) before and after the overnight feed.

We will not exceed 10,000 lipase units/kg/day or 4000 lipase units/grams of fat/day for any subject¹³. Each subject will receive pancreatic enzyme medication for a total of ten days. They will start Creon™ 4 days prior to study visit #2, they day of study visit #2, and then for five days after the visit until they have completed the second stool collection.

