8 SAFETY MANAGEMENT

8.1 Clinical Adverse Events

Clinical adverse events (AEs) will be monitored throughout the study.

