- The participants receiving pancreatic enzyme medication prior to enrolling in the study who will discontinue use prior to the first study visit (Study Visit #1) may be at risk for signs and symptoms of fat malabsorption (described above) for nine days of the study. These nine days include the three days prior to Study Visit #1 (washout period), the day of Study Visit #1 to CHOP, and the five days of specimen collection after Study Visit #1. These participants will resume their pancreatic enzyme product and dose for the period of time between the end of the nine days encompassing Study Visit #1 and the start of the three days prior to Study Visit #2 when they will switch to Creon™ at doses prescribed based on the study protocol. Therefore, they will not be at increased risk for the signs and symptoms of fat malabsorption during the time between visits or during the ten days encompassing Study Visit #2 as they will be taking pancreatic enzyme medication throughout this period. When the study is completed, these participants will discontinue Creon™ and resume their usual care and resume their usual pancreatic enzyme product and dose.
- The participants who are naïve to pancreatic enzyme medication prior to entering the study, will take Creon™ for the ten days encompassing Study Visit #2 of the study, that is, four days prior to the protocol visit to CHOP, the day of the visit, and then five days after the visit until all specimen collections have been completed. If these participants have undiagnosed reduced pancreatic function and reduced fat absorption, they may have increased risk for the signs and symptoms of fat malabsorption upon discontinuation of

Creon™ at the end of the study. If their pancreatic function and fat absorption is normal, withdrawal from Creon™ at the end of the study will not increase their risk for these symptoms.

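### The adverse-event diary is not scheduled for the first four days on Creon or for the enzyme washout days, so capture on those days relies on short recall and undated phone contacts

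*Combined protocol and SAP*

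**What the plan says.** - **General commitment.** Section 8.1 states: "Clinical adverse events (AEs) will be monitored throughout the study". Section 8.3 requires each event to be recorded with, among other items, its onset date and time, intensity, duration and causality.
- **Diary days.** The instruction "Maintain adverse events diary" appears on Days 9-13 in all four Visit 1 lists (Section 4.2) and on Days 6-10 in both Visit 2 lists (Section 4.4). It appears on no other day. Diary instructions are first given on Day 8, at Visit 1, and are given again on Creon Day 5.
- **Creon Day 5 (Visit 2).** The list includes "Adherence to pancreatic enzyme medication and Adverse Events Questionnaires".
- **Washout.** For prior enzyme users outside the MBT/CCK subset, the whole entry for Days 5-7 reads "Discontinue pancreatic enzyme medication (Washout) Subject's normal diet". The MBT/CCK washout list has no diary line on these days either. Section 9.4.2 says prior users "may be at risk for signs and symptoms of fat malabsorption (described above) for nine days of the study", counting the washout in those nine days.
- **Other capture.** Table 1 and Section 5.1.3 place adverse-event questioning at Visits 1, 2 and 3. Section 5.1.3 adds that adherence contacts, including phone calls, also collect adverse events. The Monitoring Plan and Section 9.4.1 describe ongoing collection with weekly review.
- **Reporting.** Section 5.3, repeated in the Safety Analysis under Section 6.3, says: "The frequencies of AEs by type, body system, severity and relationship to study supplement will be summarized". No breakdown by study period is specified.
- **Duration.** Section 7.1.3 says: "Each subject will receive pancreatic enzyme medication for a total of ten days". The opening of Section 4.4 says subjects "will receive this therapy for nine days encompassing Study Visit #2".

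**The concern.** Followed as written, the plan has no prospective daily record for the start of treatment or the start of enzyme withdrawal. Mild events that begin and settle within a few days are the ones recall is most likely to miss, and recall is a poor source for an onset time or a duration. Some subjects are as young as four.

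Onset timing matters here because the event profiles overlap. Section 9.4.2 lists abdominal pain, flatulence and abnormal bowel movements for Creon; cramping, gas and loose stools for enzyme withdrawal; and much the same for the MBT meal. With no control arm and open-label dosing, timing is the main objective means of telling these apart. The causality judgement in the planned summary also depends on it.

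The visit-based safeguard is incomplete too. Table 1 and Section 5.1.3 put an adverse-event question at Visit 1, but none of the four Day 8 lists contains one.

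**Working it through.** Only day counts apply; no power or sample-size formula bears on this point.

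**The plan's own durations**
- Creon (Section 7.1.3): 4 days before Visit 2 + 1 visit day + 5 days after = 10. This matches the stated ten days and the Day 1-10 lists in Section 4.4. It does not match the nine days in the opening sentence of Section 4.4.
- Off-enzyme period for prior users (Section 9.4.2): 3 washout days + 1 visit day + 5 collection days = 9. This matches Days 5-13 in Section 4.2.

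**Creon block (Section 4.4 numbering)**
- Days with a diary: 6, 7, 8, 9, 10, which is 5 of 10 (50%).
- Days without a diary: 1, 2, 3, 4, 5.
- Day 5 has a same-day questionnaire, so Days 1-4 have neither.
- Recall at Visit 2 runs from 5 − 4 = 1 day to 5 − 1 = 4 days.

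**Off-enzyme block, prior users (Section 4.2 numbering)**
- Days with a diary: 9, 10, 11, 12, 13, which is 5 of 9 (56%).
- Days without a diary: 5, 6, 7, 8.
- Day 8 is Visit 1. If the question in Table 1 and Section 5.1.3 is asked, Days 5-7 are left, with recall from 8 − 7 = 1 day to 8 − 5 = 3 days. If staff follow the Day 8 list alone, no question is asked.

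**Subjects stopping a drug that alters fat absorption**
- Section 4.3 has them stop 7 days before Visit 1, that is Days 1-7. None of these days has a diary line, and recall at Visit 1 reaches back 8 − 1 = 7 days.

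**Sensitivity to the schedule conflict**
- Tables 3 and 4 put Visit 2 on Day 4 of Creon; Section 4.4 puts it on Day 5. On the tables' numbering the recall span at Visit 2 is at most 4 − 1 = 3 days.
- Section 9.4.2 has prior users starting Creon three days before Visit 2 and enzyme-naïve subjects four days before.
- The pre-visit gap is therefore three or four days depending on the text used. It exists under every version.

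**Coverage if the diary ran from the first washout day and from Creon Day 1**
- Creon: 10 of 10 days instead of 5 of 10.
- Off-enzyme: 9 of 9 days instead of 5 of 9.

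**The case against.** The strongest reply is that the diary is one of several tools. Subjects are questioned at three visits, phone contacts also collect events, collection is ongoing with weekly review, and the recall spans are short. Diary instructions are given before Creon starts and nothing tells subjects to stop between blocks, so the missing lines on Creon Days 1-4 may be a drafting omission. The washout gap affects only prior enzyme users, whose number the documents do not give. The study is a 26-subject exploratory trial and the CFA endpoint is untouched.

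Much of this stands and limits the size of the point. It does not close the gap: the phone contacts have no dates, are tied to enzyme adherence and do not clearly reach the washout, and the day lists are the only place where diary days are set.

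A reader might also infer four stronger conclusions that the documents do not support:
- **That Section 8.1 is contradicted.** Monitoring throughout the study does not promise a daily diary.
- **That the first five Creon days rest on recall.** Day 5 has its own questionnaire; the gap is Days 1-4.
- **That the gap favours Creon.** No off-versus-on comparison of adverse events is planned. Five diary days are listed in each block, and for prior users the start of the off-enzyme period is also missing, so onset days are lost on both sides. No direction of bias is established.
- **That all events must be pooled in one table.** The safety text specifies no period split, but does not forbid one, and the onset dates required by Section 8.3 would allow it.

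Calling the uncovered days those of greatest safety interest would also be a judgement: Section 9.4.2 gives no timing for Creon effects and treats all nine off-enzyme days as at risk.

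**Conclusion.** The point holds as a gap in collection method. As scheduled, adverse-event capture is uneven across days: four Creon days including the first dose, and three washout days in prior enzyme users, have no diary and no same-day question. These days depend on recall of at most four and three days respectively, plus undated calls. That is weak support for the onset, intensity and duration data that Section 8.3 requires for every event.

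This assumes that sites follow the day lists literally and that the numbering in Section 4.4 applies. If subjects in practice keep the diary continuously from Visit 1, the Creon part of the gap disappears, but the plan should say so. The washout part remains in either case, because the instructions come too late. The day counts are certain; how many events would be missed cannot be estimated from the documents. The change is worth making because it is specific and cheap, but nothing here threatens the primary analysis.

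**What to change.** - **Creon block.** Add the diary line to Days 1-5 in both Visit 2 lists of Section 4.4. Drug and diary instructions are already provided at Visit 1, so no new contact is needed.
- **Before Visit 1.** For subjects who stop enzymes or a drug that alters fat absorption, provide the diary with the consent form, which must already be signed before discontinuation, and run it from the first day of discontinuation. For all others, start it at Visit 1.
- **Visit 1.** Add the adverse-event question to the four Day 8 lists, to match Table 1 and Section 5.1.3.
- **Reporting.** In Sections 5.3 and 6.3, add a tabulation by period of onset (before Creon, on Creon, after Creon, with washout and MBT days identifiable), using the onset dates Section 8.3 already requires.
- **Reconcile.** Settle the Visit 2 day (Tables 3-4 against Section 4.4) and the nine against ten Creon days, so that the diary days are unambiguous. This review takes no position on which is right.

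**Cost.** Edits to six day lists and one extra table split. Subjects keep the diary for about 5 more days on Creon. Those who stop a drug also keep it between discontinuation and Visit 1: 3 days for enzymes, about 7 for drugs that alter fat absorption.
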